## **8.1. Efficacy Assessments**

Not applicable.

## **8.2. Safety Assessments**

Planned time points for all safety assessments are provided in the [SoA](#). Unscheduled clinical laboratory measurements may be obtained at any time during the study to assess any perceived safety issues.

### **8.2.1. Physical Examinations**

A complete physical examination will include, at a minimum, head, ears, eyes, nose, mouth, skin, heart and lung examinations, lymph nodes, and gastrointestinal, musculoskeletal, and neurological systems.

A brief physical examination will include, at a minimum, assessments of general appearance, the respiratory and cardiovascular systems, and participant-reported symptoms.

Physical examinations may be conducted by a physician, trained physician's assistant, or nurse practitioner as acceptable according to local regulation.

Height and weight will also be measured and recorded as per the [SoA](#). For measuring weight, a scale with appropriate range and resolution is used and must be placed on a stable, flat surface. Participants must remove shoes, bulky layers of clothing, and jackets so that only light clothing remains. They must also remove the contents of their pockets and remain still during measurement of weight.

Physical examination findings collected during the study will be considered source data and will not be required to be reported, unless otherwise noted. Any untoward physical examination findings that are identified during the active collection period and meet the definition of an AE or SAE ([Appendix 3](#)) must be reported according to the processes in [Sections 8.3.1 to 8.3.3](#).

### **8.2.2. Vital Signs**

Supine BP will be measured with the participant's arm supported at the level of the heart and recorded to the nearest mm Hg after approximately 5 minutes of rest. The same arm (preferably the dominant arm) will be used throughout the study. Participants should be instructed not to speak during measurements.

The same properly sized and calibrated BP cuff will be used to measure BP each time. The use of an automated device for measuring BP and pulse rate is acceptable; however, when done manually, pulse rate will be measured in the brachial/radial artery for at least 30 seconds. When the timing of these measurements coincides with a blood collection, BP and pulse rate should be obtained prior to the nominal time of the blood collection.

Additional collection times, or changes to collection times, of BP and pulse rate will be permitted, as necessary, to ensure appropriate collection of safety data.

#### **8.2.2.1. Respiratory Rate**

Respiratory rate will be measured after approximately 5 minutes of rest in a supine position by observing and counting the respirations of the participant for 30 seconds and multiplying by 2. When BP is to be taken at the same time, respiration measurement will be done during the 5 minutes of rest and before BP measurement.

### **8.2.2.2. Temperature**

Temperature will be measured orally. No eating, drinking, or smoking is allowed for 15 minutes prior to the measurement. Temperature will be measured as per CRU standard practice.

### **8.2.3. Electrocardiograms**

Standard 12-lead ECGs utilizing limb leads (with a 10 second rhythm strip) should be collected at times specified in the [SoA](#) section of this protocol using an ECG machine that automatically calculates the heart rate and measures PR, QT, and QTc intervals and QRS complex. Alternative lead placement methodology using torso leads (eg, Mason-Likar) should not be used given the potential risk of discrepancies with ECGs acquired using standard limb lead placement. All scheduled ECGs should be performed after the participant has rested quietly for at least 5 minutes in a supine position.

To ensure safety of the participants, a qualified individual at the investigator site will make comparisons to baseline (Period 1, Day 1) measurements. Additional ECG monitoring will occur if a) a postdose QTcF interval is increased by  $\geq 60$  msec from the baseline **and** is  $>450$  msec; or b) an absolute QT value is  $\geq 500$  msec for any scheduled ECG. If either of these conditions occurs, then 2 additional ECGs will be collected approximately 2 to 4 minutes apart to confirm the original measurement. If the QTc values from these repeated ECGs remain above the threshold value, then a single ECG must be repeated at least hourly until QTc values from 2 successive ECGs fall below the threshold value that triggered the repeat measurement.

If a) a postdose QTcF interval remains  $\geq 60$  msec from the baseline **and** is  $>450$  msec; or b) an absolute QT value is  $\geq 500$  msec for any scheduled ECG for greater than 4 hours (or sooner, at the discretion of the investigator); or c) QTcF intervals get progressively longer, the participant should undergo continuous ECG monitoring. A cardiologist should be consulted if QTcF intervals do not return to less than the criteria listed above after 8 hours of monitoring (or sooner, at the discretion of the investigator).

In some cases, it may be appropriate to repeat abnormal ECGs to rule out improper lead placement as contributing to the ECG abnormality. It is important that leads be placed in the same positions each time in order to achieve precise ECG recordings. If a machine-read QTc value is prolonged, as defined above, repeat measurements may not be necessary if a qualified medical provider's interpretation determines that the QTcF values are in the acceptable range.

ECG values of potential clinical concern are listed in [Appendix 7](#).

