#### **Diagnostic Assessments:**

11. A positive urine drug test.
12. Screening supine BP  $\geq 140$  mm Hg (systolic) or  $\geq 90$  mm Hg (diastolic), following at least 5 minutes of supine rest. If BP is  $\geq 140$  mm Hg (systolic) or  $\geq 90$  mm Hg (diastolic), the BP should be repeated 2 more times and the average of the 3 BP values should be used to determine the participant's eligibility.
13. Baseline standard 12-lead ECG that demonstrates clinically relevant abnormalities that may affect participant safety or interpretation of study results (eg, baseline QTcF interval  $>450$  msec, complete LBBB, signs of an acute or indeterminate-age myocardial infarction, ST-T interval changes suggestive of myocardial ischemia, second- or third-degree AV block, or serious bradyarrhythmias or tachyarrhythmias). If the baseline uncorrected QT interval is  $>450$  msec, this interval should be rate-corrected using the Fridericia method and the resulting QTcF should be used for decision making and reporting. If QTcF exceeds 450 msec, or QRS exceeds 120 msec, the ECG should be repeated 2 more times and the average of the 3 QTcF or QRS values should be used to determine the participant's eligibility. Computer-interpreted ECGs should be overread by a physician experienced in reading ECGs before excluding a participant.
14. Participants with **ANY** of the following abnormalities in clinical laboratory tests at screening, as assessed by the study-specific laboratory and confirmed by a single repeat test, if deemed necessary:
  - AST **or** ALT level  $\geq 1.25 \times$  ULN;
  - Total bilirubin level  $\geq 1.5 \times$  ULN; participants with a history of Gilbert's syndrome may have direct bilirubin measured and would be eligible for this study provided the direct bilirubin level is  $\leq$  ULN.

PFIZER CONFIDENTIAL

- eGFR <90 mL/min/1.73 m^2 with 10% variation based on the CKD-EPI equation.

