## 10.7. Appendix 7: ECG Findings of Potential Clinical Concern

ECG Findings That May Qualify as AEs

Marked sinus bradycardia (rate <40 bpm) lasting minutes.

New PR interval prolongation >280 msec.

New prolongation of QTcF to >480 msec (absolute) or by <math>\geq</math>60 msec from baseline.

New-onset atrial flutter or fibrillation, with controlled ventricular response rate: ie, rate <120 bpm.

New-onset type I second-degree (Wenckebach) AV block of >30 seconds' duration.

Frequent PVCs, triplets, or short intervals (<30 seconds) of consecutive ventricular complexes.

ECG Findings That May Qualify as SAEs

QTcF prolongation >500 msec.

New ST-T changes suggestive of myocardial ischemia.

New-onset left bundle branch block (QRS >120 msec).

New-onset right bundle branch block (QRS >120 msec).

Symptomatic bradycardia.

Asystole:

In awake, symptom-free participants in sinus rhythm, with documented periods of asystole <math>\geq</math>3.0 seconds or any escape rate <40 bpm, or with an escape rhythm that is below the AV node.

In awake, symptom-free participants with atrial fibrillation and bradycardia with 1 or more pauses of at least 5 seconds or longer.

Atrial flutter or fibrillation, with rapid ventricular response rate: rapid = rate >120 bpm.

Sustained supraventricular tachycardia (rate >120 bpm) ("sustained" = short duration with relevant symptoms or lasting >1 minute).

- Ventricular rhythms >30 seconds' duration, including idioventricular rhythm (heart rate <40 bpm), accelerated idioventricular rhythm (HR >40 bpm to <100 bpm), and monomorphic/polymorphic ventricular tachycardia (HR >100 bpm (such as torsades de pointes)).
- Type II second-degree (Mobitz II) AV block.
- Complete (third-degree) heart block.

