HCoV-229E	human coronavirus 229E
HCoV-HKU1	human coronavirus HKU1
HCoV-NL63	human coronavirus NL63
HCoV-OC43	human coronavirus OC43
HCV	hepatitis C virus
HCVAb	hepatitis C antibody
HIV	human immunodeficiency virus
HR	heart rate
HRT	hormone replacement therapy
IB	Investigator's Brochure
ICD	informed consent document
ICH	International Council for Harmonisation of Technical Requirements for Pharmaceuticals for Human Use
ID	identification
IND	Investigational New Drug
INR	international normalized ratio
IPAL	Investigational Product Accountability Log
IQMP	Independent Qualified Medical Practitioners
IRB	Institutional Review Board
IV	Intravenous(ly)
$k_{el}$	terminal phase rate constant calculated by a linear regression of the log-linear concentration-time curve.

Abbreviation	Term
K i	inhibition constant
LBBB	left bundle branch block
LFT	liver function test
MAD	multiple ascending dose
MCH	mean corpuscular hemoglobin
MCHC	mean corpuscular hemoglobin concentration
MCV	mean corpuscular volume
MERS	Middle East Respiratory Syndrome
msec	millisecond
n	number of participants
N/A	not applicable
NHP	non-human primate
NOAEL	no observed adverse effect level
PCR	polymerase chain reaction
PD	pharmacodynamic(s)
PE	physical examination
pH	potential of hydrogen
PK	pharmacokinetic(s)
PR	pulse rate
PT	prothrombin time
PT-INR	prothrombin time-international normalized ratio
PVC	premature ventricular contraction/complex
q12h	every 12 hours
QT	time from the beginning of the QRS complex to the end of the T wave
QTc	corrected QT interval
QTcF	QTc corrected using Fridericia's formula
qual	qualitative
RBC	red blood cell
R ac	accumulation ratio
R ac,Cmax	accumulation ratio based on C max :
RR	respiratory rate
RT-PCR	reverse-transcriptase polymerase chain reaction
SAD	single ascending dose
SAE	serious adverse event
SAP	Statistical Analysis Plan
SARS-CoV-1	severe acute respiratory syndrome coronavirus 1
SARS-CoV-2	severe acute respiratory syndrome coronavirus 2
SCr	serum creatinine
SoA	schedule of activities
SOP	standard operating procedure
SRSD	single-reference safety document
SUSAR	Suspected Unexpected Serious Adverse Reaction
t ½	terminal elimination half-life
TBili	total bilirubin
TEAE	treatment emergent adverse event
THC	tetrahydrocannabinol
T max	time to reach C max

Abbreviation	Term
TSH	thyroid stimulating hormone
ULN	upper limit of normal
US	United States

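### Section 8.2.3 sets its 500-msec ECG rules on uncorrected QT, so some QTcF values above 500 msec trigger no repeat ECG

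*Protocol*

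**What the plan says.** Protocol Section 8.2.3 gives two triggers for repeat ECGs. Trigger (a) needs a QTcF rise of at least 60 msec from the Period 1 Day 1 baseline together with a QTcF above 450 msec. Trigger (b) fires when "an absolute QT value is" at least 500 msec. The continuous-monitoring rule has its own (b), with the same raw-QT threshold: "msec for any scheduled ECG for greater than 4 hours".

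The abbreviation list in Appendix 8 defines QT as the "time from the beginning of the QRS complex to the end of the T wave", which is the uncorrected interval, and lists QTc and QTcF separately.

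The steps around (b) use a corrected interval:

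- Confirmation, and the start of hourly ECGs: "If the QTc values from these repeated ECGs remain above the threshold value, then a single ECG must be repeated at least hourly". The hourly series also stops on QTc.
- Continuous-monitoring criterion (c) uses progressively longer QTcF.
- Cardiologist referral: "A cardiologist should be consulted if QTcF intervals do not return to less than the criteria listed above after 8 hours of monitoring".
- The over-read sentence lets repeats be skipped if a qualified provider's "interpretation determines that the QTcF values are in the acceptable range".
- Exclusion 13 in Section 5.2, for a raw QT above 450 msec: "this interval should be rate-corrected using the Fridericia method and the resulting QTcF should be used for decision making and reporting".
- Appendix 7 lists "QTcF prolongation" above 500 msec among findings that may qualify as SAEs, and SAP Appendix 1 has a QTcF category above 500 msec.

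**The concern.** Section 8.2.3 has no absolute trigger on QTcF, although QTcF above 500 msec is the level that Appendix 7 and the SAP single out. Raw QT and QTcF agree only at 60 bpm, and the mismatch works in both directions.

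At higher heart rates, raw QT is shorter than QTcF. A QTcF above 500 can then escape (b), and it escapes (a) as well when the rise is below 60 msec. No repeat ECG is then required. This is the consequence that matters.

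At lower heart rates, raw QT is longer than QTcF, so (b) can fire on a QTcF below 500. The repeats would not confirm on QTc and no hourly series would follow. The usual cost is at most two extra ECGs, which the over-read sentence lets a provider waive.

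**Working it through.** The documents give no computed figure on this point, so there is nothing to reproduce.

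**Inputs.** Triggers (a) and (b) come from Protocol 8.2.3. The baseline limit of QTcF 450 msec comes from exclusion 13. The level of concern, QTcF above 500 msec, comes from Appendix 7. Fridericia is the only correction the documents name; its standard form is QTcF = QT / (60/HR)^(1/3), so QT = QTcF × (60/HR)^(1/3).

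**When (a) stays silent.** QTcF above 500 already exceeds 450, so (a) fails only if the rise is below 60 msec. In whole msec, the post-dose QTcF must lie between 501 and baseline + 59. For baselines of 442 or more, the number of such values is (baseline + 59) − 501 + 1 = baseline − 441.

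| Baseline QTcF | QTcF values that escape (a) | Count |
|---|---|---|
| 441 or less | none | 0 |
| 442 | 501 | 1 |
| 446 | 501-505 | 5 |
| 450 | 501-509 | 9 |

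Over baselines 442 to 450 the sum is 1 + 2 + … + 9 = 45 combinations. The rise runs from 501 − 450 = 51 to 509 − 450 = 59 msec.

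**When (b) stays silent.** QT < 500 exactly when HR > 60 × (QTcF/500)^3.

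| QTcF | HR above which QT < 500 | QT at 80 bpm |
|---|---|---|
| 501 | 60.4 bpm | 455.2 |
| 505 | 61.8 bpm | 458.8 |
| 509 | 63.3 bpm | 462.5 |

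**Both together.** Of the 45 combinations, the number that fire neither trigger is 0 at 60 bpm, 17 at 61, 35 at 62, 44 at 63, and all 45 at 64 bpm or more. Example: baseline 446, post-dose QTcF 505, 80 bpm. The rise is 59, so (a) does not fire. QT is 458.8, so (b) does not fire.

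**With QTcF ≥ 500 in (b).** All 45 fire at any heart rate, so none is missed. The same holds if (b) reads *QT or QTcF*.

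**Low-rate direction.** Below 60 bpm, (b) fires on a QTcF under 500 whenever QT lies from 500 up to 500 × (60/HR)^(1/3). That upper bound is 550.3 at 45 bpm, 531.3 at 50, 514.7 at 55 and 502.8 at 59. Example: QT 510 at 50 bpm is QTcF 479.9.

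**Reach.** The Schedule of Activities (footnote l) has one routine post-dose ECG, on Period 2 Day 3. That is 48 h after PF-07321332 and 48 − 12 = 36 h after the last ritonavir dose. An early-termination ECG may be added. About 12 participants are planned.

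**The case against.** **The section plainly means a corrected interval.** Confirmation, stopping and referral all use QTc or QTcF, and the over-read sentence speaks of a prolonged machine-read QTc as though the triggers had defined one. On this view (b) is a drafting slip that staff would read correctly. A slip is indeed the likeliest explanation. But no sentence redefines (b), the abbreviation list says raw QT, and a written safety threshold should not depend on staff inferring another variable.

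**A QTcF of 501-509 would be noticed anyway.** Appendix 7 flags it. The site compares each ECG with baseline. The investigator must follow up AEs and arrange further measurements as medically indicated. Safety issues go to the sponsor at once, and a participant may be kept in the CRU (Section 4.1). This stands as mitigation. These routes depend on judgement or are only recommended, however, and none requires the repeat ECGs. Criterion (c) needs serial ECGs, which the schedule does not supply.

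**The practical reach is close to nil.** Forty-eight hours is 48/13 = 3.7 to 48/6 = 8 half-lives, using the 6 to 13 h in Section 4.2, so roughly 8% or less of the drug remains. The missed case also needs a baseline within 8 msec of the limit. This stands. The count of 45 describes the width of the gap and is not a probability.

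**The bounds are not exact.** The proposed rule fires at 500 or more, while the count starts above 500. At QTcF of exactly 500, baselines 441-450 (rises 50-59) add 10 further pairs above 60 bpm. In addition, the comparison baseline is the Day 1 ECG, and the documents do not clearly say that a Day 1 pre-dose QTcF above 450 excludes a participant. Both points are fair, and both widen the gap.

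**Conclusion.** The concern holds. As written, both (b) rules in Section 8.2.3 act on raw QT while the steps that depend on them act on QTc or QTcF. The result is a narrow band in which QTcF exceeds 500 msec and no repeat ECG is required: QTcF 501-509, baseline 442-450, rise 51-59 msec, with heart rate above 60.4 to 63.3 bpm depending on QTcF.

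This rests on three assumptions: the literal reading of QT, the Fridericia correction, and a Day 1 baseline no higher than 450 msec. If baselines above 450 occur, the band is wider.

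The chance that any of about 12 healthy participants falls in the band is very small; the documents give no data from which to estimate it. This is a minor correction to a safety rule. It should be made because it closes a gap at the protocol's own level of concern for almost no cost.

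**What to change.** In Protocol Section 8.2.3:

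- Replace *absolute QT value* with *absolute QTcF value* in repeat trigger (b) and in continuous-monitoring rule (b).
- Replace *QTc* with *QTcF* at both places in the confirmation and stopping sentence. This is editorial, since Fridericia is the only correction named.

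That is four word replacements. The machine already reports heart rate, QT and QTc, and trigger (a) already needs QTcF, so no new procedure or data are required. Exclusion 13, Appendix 7 and the SAP need no change.

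The trade-off is losing the raw-QT alarm below 60 bpm. The loss is small, because exclusion 13 and the over-read sentence already make QTcF the deciding value. A sponsor that wants to keep the alarm can write *absolute QT or QTcF value* in the repeat trigger only. This closes the high-rate gap equally well, but a repeat set off by raw QT alone would still be confirmed on QTcF.

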### **8.2.4. Clinical Safety Laboratory Assessments**

See [Appendix 2](#) for the list of clinical safety laboratory tests to be performed and the [SoA](#) for the timing and frequency. All protocol-required laboratory assessments, as defined in [Appendix 2](#), must be conducted in accordance with the laboratory manual and the [SoA](#).

Unscheduled clinical laboratory measurements may be obtained at any time during the study to assess any perceived safety issues.

The investigator must review the laboratory report, document this review, and record any clinically relevant changes occurring during the study in the AE section of the CRF.

Clinically significant abnormal laboratory findings are those which are not associated with the underlying disease, unless judged by the investigator to be more severe than expected for the participant's condition.

All laboratory tests with values considered clinically significantly abnormal during participation in the study or within 48 hours after the last dose of study intervention should be repeated until the values return to normal or baseline or are no longer considered clinically significant by the investigator or medical monitor.

If such values do not return to normal/baseline within a period of time judged reasonable by the investigator, the etiology should be identified and the sponsor notified.

See [Appendix 6](#) for suggested actions and follow-up assessments in the event of potential drug-induced liver injury.

Urine drug (mandatory) and alcohol breath test (at discretion of investigator) will be performed at screening and on Day -1. These tests may be performed at any other time at the discretion of the investigator.

#### **8.2.5. COVID-19 specific assessments**

Participants will be checked exposure to positive participant, residence or travel in area of high incidence and COVID-19 related signs and symptoms. Participants will be tested for SARS-COVID-19 infection by PCR prior to being admitted to the clinic for confinement and a subsequent COVID-19 test will be performed after 4 days (ie, upon completion of 4 x 24 hours in house), or if they develop COVID-19 like symptoms. Additional testing may be required by local regulations or by the Principal Investigator.

#### **8.2.6. Pregnancy Testing**

Pregnancy tests may be urine or serum tests, but must have a sensitivity of at least 25 mIU/mL. Pregnancy tests will be performed in WOCBP at the times listed in the [SoA](#). Following a negative pregnancy test result at screening, appropriate contraception must be commenced and a second negative pregnancy test result will be required at the baseline visit prior the participant's receiving the study intervention. Pregnancy tests will also be done whenever 1 menstrual cycle is missed during the active treatment period (or when potential pregnancy is otherwise suspected) and at the end of the study. Pregnancy tests may also be repeated if requested by IRBs/ECs or if required by local regulations. If a urine test cannot be confirmed as negative (eg, an ambiguous result), a serum pregnancy test is required. In such cases, the participant must be excluded if the serum pregnancy result is positive.

### **8.3. Adverse Events, Serious Adverse Events, and Other Safety Reporting**

The definitions of an AE and an SAE can be found in [Appendix 3](#).

AEs may arise from symptoms or other complaints reported to the investigator by the participant (or, when appropriate, by a caregiver, surrogate, or the participant's legally authorized representative), or they may arise from clinical findings of the Investigator or other healthcare providers (clinical signs, test results, etc.).

The investigator and any qualified designees are responsible for detecting, documenting, and recording events that meet the definition of an AE or SAE and remain responsible to pursue and obtain adequate information both to determine the outcome and to assess whether the event meets the criteria for classification as an SAE or caused the participant to discontinue the study intervention (see [Section 7.1](#)).

During the active collection period as described in Section 8.3.1, each participant will be questioned about the occurrence of AEs in a nonleading manner.

In addition, the investigator may be requested by Pfizer Safety to obtain specific follow-up information in an expedited fashion.

